#### 6.2.3.2. Sensitivity and Supportive Analyses

- *Supportive*: For each CSM at Week 52, the frequency and proportion of participants in each improvement category (as defined in [Section 9.3](#)) will be reported.
- *Supportive*: Summary statistics for the absolute value of each CSM, including the sample size, mean, standard deviation, median, minimum, and maximum at the baseline and postbaseline visits will also be presented.

### 6.3. Other Endpoint(s)

#### 6.3.1. PK Endpoints

- Analysis populations: PK concentration population.
- Analysis time points: all times with PK samples taken.

- Analysis methodology: summary statistics will be provided for serum concentrations.
- Reporting results: Presentations for PF-06823859 concentrations will include:
  - a listing of all concentrations sorted by participant ID, cohort, and nominal time post-dose. The concentration listing will also include the actual times. Deviations from the nominal time will be given in a separate listing.
  - a summary of concentrations by nominal time post-dose, where the set of statistics will include n, mean, median, standard deviation, coefficient of variation (CV), minimum, maximum, and the number (percentage) of concentrations above the lower limit of quantification (LLQ).
  - median concentrations time plots (semi-log scale) against nominal time post-dose.
  - mean concentrations time plots (semi-log scale) against nominal time post-dose.
  - individual concentration time plots by participant (on semi-log scale) against actual time post-dose (there will be separate plots for each participant per scale).

The length of time used for the x-axes of these plots will be decided on review of the data, and will depend on how long the respective PK concentration is quantifiable in the matrix. For summary statistics, median and mean plots by sampling time, the nominal PK sampling time will be used, for individual participant plots by time, the actual PK sampling time will be used.

If data permits, non-compartmental PK parameters may be derived from the PF-06823859 serum concentrations.

Population PK modeling may be performed with the concentration data from this study alone or combined with data from other studies. In addition, a relationship between exposures and efficacy/safety endpoints may be evaluated using population PK/PD approach. Any population analyses conducted will not be part of the clinical study report (CSR) and may be reported separately.

#### 6.3.2. PD Endpoints, including Selected Biomarkers (hsCRP, total IFN $\beta$ )

- Analysis population: biomarker analysis population.
- Analysis time points: all visits with samples taken.
- Analysis methodology: summary statistics. The change from baseline may also be investigated by applying the LANCOVA model (as described in [Section 5.2.1](#)). The

log-transformation of the outcomes may be applied to the original observations after analysis of the distribution of observed data.

- Descriptive statistics for absolute values, change from baseline, percent change from baseline will include sample size, mean, standard deviation, median, minimum and maximum by visit.
- Presentations for biomarker concentrations will also include:
  - A listing of all concentrations sorted by participant ID, cohort, and nominal time post-dose. The concentration listing will also include the actual times. Deviations from the nominal time will be given in a separate listing.
  - A summary of concentrations by nominal time post-dose, where the set of statistics will include n, mean, median, standard deviation, CV, minimum, maximum and the number of concentrations above the lower limit of quantification.
  - Median concentrations time plots (semi-log scale) against nominal time post-dose.
  - Mean concentrations time plots (semi-log scale) against nominal time post-dose.
  - Individual concentration time plots by participant (semi-log scales) against actual time post-dose will be presented.

Additional biomarkers may be reported an additional exploratory analysis report.

### 6.3.3. Immunogenicity

Immunogenicity will be assessed through analysis of ADAs and NAbs.

- Analysis population: immunogenicity assessment population.
- Analysis time points: all visits with samples taken.
- Analysis methodology: summary statistics.
- Reporting results: The incidence of development of ADA NAb against PF-06823859 will be presented. Presentations for immunogenicity will include:
  - Summary of ADA and Nab analysis by sample and participant;
  - Summary of cumulative incidence of ADA and NAb over time;
  - Summary of ADA and NAb incidence and titers over time;

PFIZER GENERAL BUSINESS  
TMF Doc ID: 98.03

The official version of this form is located in the electronic document management system.

DMB02-GSOP-RF02 6.0 *Statistical Analysis Plan Template* 01-Jul-2021

- Summary of time to first ADA and NAb occurrence;
- Impact of ADA and NAb status of PF-06823859 concentrations (data permitting);
- Impact of ADA and NAb status on biomarkers (data permitting);
- Impact of ADA and NAb status on CDASI (data permitting);
- Combined plot of PK, PD (total IFN $\beta$ ), ADA and NAb response over time (data permitting).

#### 6.3.4. C-SSRS

For each of the observation times the descriptive statistics will show number of participants in the data set and proportion of participants who completed suicide, attempted suicide had preparatory acts towards imminent suicide behavior, suicidal ideation or self-injurious behavior without suicidal attempt in both cohorts.

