a. Any participant who prematurely withdraws from the treatment period should undergo the procedures for an early termination visit and return for follow up visits. At the time of the early termination visit, blood samples will be collected for PK and PD analysis. As with all PK and PD assessments, the date and time of the last dose and time of the sample collection should be captured and reported.

- b. Inclusion and exclusion criteria need to be reviewed to ensure participant is eligible for the study. No CRF will be completed, however source documentation is required to reflect that participant is eligible for study participation.
- c. Medical History for this study is any ongoing adverse events from the previous study. Please record only ongoing adverse events from the previous study onto the medical history page, so that these can be monitored. Any AEs occurring after receiving study drug administration will be considered an AE for this study.
- d. The C-SSRS will be used to assess suicidal ideation and behavior during the conduct of the study. At any visits, if there are “yes” answers on items 4, 5 or on any suicidal behavior question of the C-SSRS, the participant will be discontinued from treatment and referred to a mental health professional for appropriate evaluation and treatment. Please see [Section 8.2.10.1](#).
- e. Physician’s Global Assessment (PhGA, VAS); This assessment should be completed by the same physician completing the CDASI.
- f. Patient reported outcomes (SF-36 v2 acute, and EQ-5D-5L & EQ-VAS) are to be completed at the clinic prior to other clinical assessments. These need to be completed in the following order SF-36 v2 acute, EQ-5D-5L & EQ-VAS.
- g. Vital Signs include blood pressure, heart rate (pulse), and temperature measured after approximately 5 minutes of rest. Participants should be seated in a chair, back supported, and arms bared (free of restrictions such as rolled-up sleeves, etc.) and supported at the level of the heart. Measurements should be taken on the same arm (preferably the non-dominant arm) at each visit throughout the study after 5-10 minutes of rest and recorded to the nearest mm Hg. Participants should refrain from smoking or ingesting caffeine during the 30 minutes prior to the measurements.
- h. Weight and height will be measured without shoes.

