8.2.10. Assessment of Suicidal Ideation and Behavior

8.2.10.1. Columbia -Suicide Severity Rating Scale (C-SSRS)

Due to the increased rate of depression in the participants diagnosed with DM, the C-SSRS will be used to assess suicidal ideation and behavior during the conduct of the study. The C-SSRS is a patient-reported questionnaire administered by the investigator or site staff that have been trained to administer the test. The C-SSRS is a validated tool to evaluate suicidal ideation and behavior.¹⁵

At any visit, if the participant answers “yes” on items 4, 5 or on any suicidal behavior question of the C-SSRS, the participant will be discontinued from treatment and referred to a mental health professional for appropriate evaluation and treatment. If the participant cannot be seen by a mental health professional within 24 hours, the participant should be sent to a local emergency room for psychiatric assessment.

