9.3.5. Other Safety Analyses

9.3.5.1. Adverse Events and Suicidality Assessments

The safety analyses will be carried out in the safety population and detailed analyses will be described in the SAP.

Data relevant to the assessment of suicidality will be mapped to the C-CASA codes. Baseline and post baseline C-SSRS data (mapped to C-CASA scores) will be summarized descriptively by treatment group at baseline and each post baseline visit. The safety analyses will be carried out in the safety population, detailed analyses will be described in the SAP.

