### 3.3.3. Columbia-Suicide Severity Rating Scale (C-SSRS)

The C-SSRS is used to assess suicidal ideation and behavior during the conduct of the study. The C-SSRS is a patient-reported questionnaire administered by the investigator or site staff that have been trained to administer the test. The absolute value and CFB in the C-SSRS will be assessed.

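### The C-SSRS summary in SAP 6.3.4 is by visit only, with all suicidal ideation in one category, so it cannot give the number of participants with any post-baseline event or show who met the protocol's item 4/5 threshold

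*SAP*

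**What the plan says.** SAP 6.3.4 is a single sentence. It begins "For each of the observation times the descriptive statistics will show number of participants in the data set and proportion of participants who completed suicide" and ends "suicidal ideation or self-injurious behavior without suicidal attempt in both cohorts". It contains no row for any event on study, no change from baseline, no level of ideation and no listing.

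SAP 3.3.3 defines the endpoint differently: "The absolute value and CFB in the C-SSRS will be assessed". This repeats the exploratory endpoint in Protocol section 3, but nothing in SAP 6.3.4 delivers the change from baseline.

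Protocol 9.3.5.1 says "Data relevant to the assessment of suicidality will be mapped to the C-CASA codes" and that the C-SSRS data "will be summarized descriptively by treatment group at baseline and each post baseline visit". It leaves the detailed analyses to the SAP. The SAP does not mention C-CASA.

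Protocol 8.2.10.1 gives the reason for the scale, "Due to the increased rate of depression in the participants diagnosed with DM", and a stopping rule: after an affirmative answer "on items 4, 5 or on any suicidal behavior question of the C-SSRS, the participant will be discontinued from treatment". The footnotes to both schedules of activities and Protocol 10.10.2 repeat this rule.

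**The concern.** Suicidality is a rare, categorical harm. A reader first wants to know how many participants had any event after starting open-label treatment, how severe the worst event was, and whether it was new since baseline. A series of by-visit proportions answers none of these, because the same person can contribute to several visits.

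The protocol also draws a line within the scale: items 4 and 5, or any behavior question, lead to treatment discontinuation. The planned table separates the behavior categories but merges all ideation, so the study's own threshold cannot be seen in the output dedicated to this endpoint.

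Third, C-SSRS is scheduled at the early-termination visit and the stopping rule applies at any visit. If the table is built only from windowed scheduled visits, some positive answers may not be counted in any row.

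**Working it through.** The plan states no figure to reproduce. There is no suicidality rate, sample-size formula or hypothesis test. The event counts below are assumptions, used only to show what the table can and cannot determine.

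**Inputs**
- Planned size: about 30 participants (Protocol 9.5). The split between cohorts is not given, so 30 is used throughout. Cohort denominators would be smaller and the percentages correspondingly larger.
- Scheduled post-baseline C-SSRS assessments: Weeks 12, 24, 36, 48, 60 and 68 in Table 1 (V = 6). Table 2 as extracted also shows Week 64 (V = 7). The tables may be damaged by extraction, so both values are carried.
- Visit windows: target day ±3 days, 7 days each, from Week 4 to Week 68 (SAP 9.1).

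**1. Number of participants affected.** Let x_j be the count with an event at visit j, and D the number of distinct participants with any event. All that follows from the table is

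max(x_j) ≤ D ≤ min(n, Σx_j).

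Take x_j = 1 at every visit and n = 30:

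| V | Lowest D | Exact 90% CI | Highest D | Exact 90% CI |
|---|---|---|---|---|
| 6 | 1/30 = 3.3% | 0.2% to 14.9% | 6/30 = 20.0% | 9.1% to 35.7% |
| 7 | 1/30 = 3.3% | 0.2% to 14.9% | 7/30 = 23.3% | 11.5% to 39.4% |

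The intervals are Clopper-Pearson. One table is thus compatible with a sixfold or sevenfold range in the number of people affected. A per-participant row would fix the count.

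**2. Ideation threshold.** A visit cell of 3/30 under suicidal ideation is compatible with 0, 1, 2 or 3 participants at item 4 or 5, that is 0% to 10% (3/30).

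**3. Assessments outside the windows.** The post-baseline period in SAP 9.1 runs from Day 2 to Day 480, or 479 days. The windows of the C-SSRS visits cover 6 × 7 = 42 days (42/479 = 8.8%) or 7 × 7 = 49 days (49/479 = 10.2%). All 17 windows together cover 17 × 7 = 119 days (119/479 = 24.8%). SAP 9.1 has no row for early-termination or unscheduled visits. Such a visit may by chance land in a scheduled window, possibly one with no planned C-SSRS; otherwise it has no observation time. These percentages describe where an assessment date can be placed. They are not the share of events missed, because a scheduled assessment may pick up earlier events and the documents do not state the recall period.

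**4. Comparison within the SAP.** SAP 6.3.3, the section immediately before, plans ADA and NAb results by sample and by participant, with cumulative incidence and time to first occurrence. SAP 6.3.4 plans none of these for suicidality.

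**5. Completed suicide.** The category is named in 6.3.4. The questionnaire is answered by the participant (Protocol 8.2.10.1), so it cannot supply this outcome. The SAP does not say which data do, or to which visit such a death is assigned.

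**The case against.** The strongest reply is that SAP 6.3.4 does what the protocol asks: Protocol 9.3.5.1 specifies a summary at baseline and at each later visit. Protocol 9.3.2 adds that all safety endpoints will be listed, and with about 30 participants a listing would show who had what. The endpoint is exploratory, in a single-arm descriptive study. Much of this stands: the by-visit table should stay, and no error rate or decision rule is affected. But the protocol leaves the detail to the SAP, and SAP 6.3.4 commits to no C-SSRS listing.

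Three stronger readings are tempting, and the documents do not support them.

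- *A completed suicide would necessarily read zero, or appear nowhere.* SAP 6.3.4 lists the category, and the protocol's C-CASA mapping is not confined to questionnaire answers; the SAP's silence on C-CASA does not withdraw it. A fatal event is an SAE (Protocol 10.3.2) and enters SAE incidence by cohort (SAP 6.6.1). Death is a reason for leaving the study (Protocol 7.2) and so enters disposition (SAP 6.5.2). The gap is only that 6.3.4 names no source or observation time.
- *The table understates the proportion affected.* A by-visit proportion makes no claim to be cumulative. It leaves the participant count unstated.
- *Ideation at the threshold is invisible.* It leads to discontinuation of treatment, which must be documented (Protocol 7.1) and is counted in SAP 6.5.2. Those counts need not identify C-SSRS as the reason, and the documents do not require a positive answer to be recorded as an AE. The information is therefore not assured, but neither is it wholly hidden.

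A reader might also take the protocol to state a raised suicide risk in dermatomyositis. It states an increased rate of depression.

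**Conclusion.** The point holds for the C-SSRS output. As written, SAP 6.3.4 cannot give the number of participants with any post-baseline event: 1/30 at each visit fits 1 to 6 people, or 1 to 7 on the Table 2 schedule as extracted. It also cannot show who met the item 4/5 threshold. Positive answers at early-termination or unscheduled visits may fall outside every row. The change from baseline promised in SAP 3.3.3 has no matching output, and the source for completed suicide is unspecified.

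The bounds depend only on the by-visit layout; the percentages assume a denominator of 30. SAP 9.1 allows slight updates to the visit assignment, so the window gap could be closed without changing anything else.

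No primary or secondary result is affected. Priority is minor to moderate: the endpoint is exploratory, but it also informs safety and the remedy is cheap.

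**What to change.** In SAP 6.3.4, keep the by-visit table that Protocol 9.3.5.1 requires and add one per-participant table per cohort:

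- Number and percentage with any post-baseline event, each participant counted once at the worst C-CASA category, with the ordering of categories stated.
- A shift from baseline category to worst post-baseline category.
- Ideation at items 4-5 shown separately from other ideation. This concerns reporting only and leaves the stopping rule as it is.
- Sources: scheduled, early-termination and unscheduled C-SSRS, plus relevant AE and SAE data, in line with the protocol's C-CASA mapping. Name the source for completed suicide.

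In SAP 9.1 or 6.3.4, say how early-termination and unscheduled assessments enter the tables. In SAP 3.3.3, state that change from baseline for C-SSRS means the categorical shift above.

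The cost is SAP wording and one small extra table per cohort, from data already collected. No new assessment is needed.

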#### 6.3.5. PROs (EQ-5D-5L, SF-36 v2 acute)

- Analysis population: Skin analysis set and muscle analysis set.
- Analysis time points: all visits with responses assessed.
- Analysis methodology: summary statistics. For the SF-36 observations, two summary component scores (PCS and MCS) and 8 scale subscores (PF, RP, BP, GH, VT, SF, RE, and MH) will be summarized. CFB will also be reported for the PCS and MCS scores. For the EQ-5D-5L, the summed number of checked boxes under each of the five sections will be reported.
- Reporting results:
  - Change from baseline: The sample size, mean, standard deviation, median, minimum and maximum by visit.
  - Absolute values: The sample size, mean, standard deviation, median, minimum and maximum by visit.

Ad-hoc analyses for PROs with minimum clinically important differences may be performed.

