
To characterize pharmacokinetics (PK) of PF-06823859.To characterize pharmacodynamics (PD) effects of PF 06823859.To evaluate immunogenicity of PF-06823859.To evaluate the effect of PF-0682359 on suicidality assessment over time in participants with active DM.To evaluate the effect of PF-0682359 on SF-36 (v2 acute) and EQ-5D-5L PROs.	
Plasma concentrations of PF-06823859.Absolute values and change from baseline in the values of selected biomarkers at all scheduled time points.Incidence of ADA and NAb.Absolute values and change from baseline values of Columbia-Suicide Severity Rating Scale (C-SSRS) at all scheduled time points.Absolute values and change from baseline in the values of PROs including SF-36 (v2 acute) and EQ-5D-5L at all scheduled timepoints.	
Not applicable.

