8.1.3.2. EuroQoL 5 Dimensions 5 Levels (EQ 5D 5L) and EQ-VAS

The EQ 5D 5L is a validated, standardized, generic instrument that is the most widely used preference based HRQoL questionnaire in cost effectiveness and HTA.^{9,10,11} It is a well established instrument to measure health states and utilities in various disease areas. The EQ-5D 5L contains 5 items that cover mobility, self-care, usual activities, pain/discomfort,

and anxiety/depression, with five response levels of severity ranging from no problems to unable to/extreme problems. The measure also includes a VAS, which records the respondent's overall current health. The vertical EQ VAS, labelled with 'The best health you can imagine' and 'The worst health you can imagine', provides a quantitative measure of the patient's perception of their overall health. The EQ-5D-5L and EQ-VAS will be collected as indicated in the [Schedule of Activities \(Section 1.3\)](#).

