### 3.3.4. PROs

- European Quality of Life – 5 Dimensions-5 Level (EQ-5D-5L) Questionnaire assesses impact on health-related quality of life in 5 domains: mobility, self-care, usual activities, pain/discomfort, and anxiety/depression. Additionally, scores from the 5 domains may be used to calculate a single index value, also known as a utility score. Higher scores indicate higher level of disability. The absolute value and CFB in the EQ-5D-5L will be assessed.
- The SF-36 v.2 (Acute version) is a 36-item generic health status measure. It measures 8 general health concepts or domains: physical functioning (PF), role physical (RP), bodily pain (BP), general health (GH), vitality (VT), social functioning (SF), role emotional (RE) and mental health (MH). These domains are also summarized as physical and mental component scores (PCS and MCS). Higher scores indicate lower level of disability. The absolute value and CFB in the SF-36 v.2 scores will be assessed.

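### The EQ-5D-5L summary in SAP 6.3.5 is a count of ticked boxes that, read literally, equals 1 for every answered section, and the SAP specifies no analysis of EQ-VAS

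*SAP*

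**What the plan says.** - **Endpoint.** Protocol Section 3 lists among the tertiary/exploratory endpoints: "Absolute values and change from baseline in the values of PROs including SF-36 (v2 acute) and EQ-5D-5L at all scheduled timepoints". SAP Section 3.3.4 repeats that the absolute value and the change from baseline in the EQ-5D-5L will be assessed.
- **Instrument.** Protocol Section 8.1.3.2 describes five items, each "with five response levels of severity ranging from no problems to unable to/extreme problems". On the visual analogue scale it adds: "The measure also includes a VAS, which records the respondent's overall current health".
- **Planned EQ-5D-5L output.** SAP Section 6.3.5 states for this instrument that "the summed number of checked boxes under each of the five sections will be reported". The reporting bullets that follow, for both PROs, read "Change from baseline: The sample size, mean, standard deviation, median, minimum and maximum by visit" and "Absolute values: The sample size, mean, standard deviation, median, minimum and maximum by visit".
- **Scores and direction.** SAP Section 3.3.4 says that the domain scores may be combined into a single index value. The next sentence is "Higher scores indicate higher level of disability". No scoring rule or value set is given.
- **EQ-VAS.** Both Schedules of Activities (Protocol Section 1.3, Tables 1 and 2) put EQ-VAS on the same row as the EQ-5D-5L, and their footnotes count it among the patient-reported outcomes. The SAP does not mention it in 3.3.4, in 6.3.5 or in its abbreviations, and no endpoint names it. Protocol Section 9.3.4 says in general terms that PRO values will be summarised descriptively at each visit.

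**The concern.** On an item with ordered severity levels, the information lies in which level is marked, not in how many marks there are. A count of marks shows whether the item was answered. A programmer who follows SAP Section 6.3.5 to the letter would produce a table with the same entry in every cell. One who does not would have to choose a scoring rule. The study is open-label and SAP Section 7 allows the sponsor to review data while it runs, so that choice could be made with results in view.

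EQ-VAS has the opposite problem: the data are collected, but the SAP has no line telling anyone to tabulate them.

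At stake are the EQ-5D-5L part of one exploratory endpoint and the use made of the EQ-VAS data. No primary or secondary analysis depends on either.

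**Working it through.** The plan states no figure for this point, and there is no sample size, power or error rate to reproduce. The check is what the specified statistic equals.

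**Inputs**
- Five sections with five response levels each (Protocol 8.1.3.2).
- Statistic: number of checked boxes in each section (SAP 6.3.5).
- Summaries: n, mean, SD, median, minimum and maximum, for value and change from baseline (SAP 6.3.5).
- Assumption: one box is ticked per answered item. This is inferred from the ordered levels and is not stated in words.

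**Step 1: one participant.** Let x be the level marked in a section (1 to 5). The box count is c = Σ over levels 1–5 of I(x = level). Exactly one term is 1, so c = 1 for any x. Over five sections the total is 5 × 1 = 5.

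**Step 2: n participants who answered.** Mean = n × 1 / n = 1. SD = √[Σ(1 − 1)² / (n − 1)] = 0. Median = minimum = maximum = 1. Change from baseline = 1 − 1 = 0, with SD 0.

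**Step 3: unanswered items.** The section is either missing, so the summaries among respondents stay as in Step 2, or it counts as 0. In the second case, if m of n answered, the mean is m/n, which is the completion rate. Any non-zero change would show that someone answered at one visit and not at the other.

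**Step 4: summing over participants instead.** The total per section is the number of respondents, which is again completion.

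**Step 5: contrast with a level score.** Illustrative data for 30 respondents, with invented level distributions at baseline and Week 52 (not trial data), gave:

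| Dimension | Box count, baseline | Box count, Week 52 | Change in count | Mean level, baseline | Mean level, Week 52 | Mean change in level |
|---|---|---|---|---|---|---|
| 1 | 1 | 1 | 0 | 2.97 | 2.07 | −0.90 |
| 2 | 1 | 1 | 0 | 2.87 | 2.23 | −0.63 |
| 3 | 1 | 1 | 0 | 3.40 | 1.90 | −1.50 |
| 4 | 1 | 1 | 0 | 3.33 | 2.60 | −0.73 |
| 5 | 1 | 1 | 0 | 3.27 | 1.90 | −1.37 |

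Changes in level are from unrounded data. The SD of the count was 0 throughout, and its sum over participants was 30 in each section at both visits. The size of the level changes means nothing in itself. The point is that responses can move clearly while the box count does not move at all.

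**Step 6: fit with the rest of the plan.** A constant cannot have a direction, so the SAP 3.3.4 statement that higher means more disability cannot describe the box count. Nor can a constant give an informative change from baseline, which Protocol Section 3 and SAP 3.3.4 both require.

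**The case against.** The strongest defence is that nobody meant a completion count. SAP 3.3.4 speaks of domain scores, gives them a direction and commits to absolute values and change, so the context points to an informative quantity. The phrase might mean the level number of the checked box, or a tally of participants by box within each section. One tick per item is also an inference.

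Much of this is fair as to intent, but it does not rescue the text. A level number is not a number of boxes. A tally by level needs the words per level, where the SAP says per section. It also does not suit a mean, SD or median. One could answer that 6.3.5 names change from baseline only for the two SF-36 component scores, but its reporting bullets are not limited to them, and 3.3.4 commits the EQ-5D-5L to change as well. Either sensible reading needs different words.

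Four stronger conclusions are tempting, and the documents do not support them:

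- **That EQ-VAS will never be analysed.** Protocol 9.3.4 plans a descriptive summary of PRO values, and the schedule footnotes count EQ-VAS as a PRO. The endpoint's list of PROs is also open-ended. This cover is thin: 9.3.4 names no instrument, and the PRO list in Protocol Section 10.1.9 omits EQ-VAS. What stands is that the SAP specifies no analysis of it.
- **That the data will yield no result.** The item responses are still collected, so a corrected table definition recovers everything.
- **That the SAP gives the index the wrong direction.** The documents give no value set and no direction for the index, and the sentence may refer to the domain scores. Only its reference is unclear.
- **That the index must be reported.** The SAP makes it optional, and the documents supply no value set.

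**Conclusion.** Wrong as written, with limited impact. The only EQ-5D-5L output to which SAP 6.3.5 commits is, read literally, 1 for every answered section, with SD 0 and change 0. It measures completion and cannot deliver the exploratory endpoint. Separately, the SAP specifies no analysis of EQ-VAS, which is left to one general sentence in the protocol.

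The conclusion on the box count rests on the literal wording and on one tick per item; unanswered items would give 0 or missing. The consequence is confined to a tertiary/exploratory, descriptive endpoint in a study that plans no hypothesis testing. No safety or secondary efficacy result is affected.

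**What to change.** 1. In SAP 6.3.5, replace the box count with the number and percentage of participants at each response level (1–5), per dimension and visit, for each cohort. If a per-person score is wanted, add the level score per dimension and its change from baseline; the listed mean, SD and median then have something to describe.
2. In SAP 3.3.4 and 6.3.5, add EQ-VAS: value and change from baseline by visit.
3. In SAP 3.3.4, state which score the direction sentence refers to. If the optional index is reported, name the value set.

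The cost is a few lines of SAP text and the matching table shells. No new data, visits or protocol amendment are needed, because the primary endpoint is untouched. It should be done before any analysis is run, so that the scoring rule does not depend on the results.
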